6.3.3.2 Handling

Infusion solutions should be prepared in **0.9% Sodium Chloride Injection, USP** (normal saline) or 5% Dextrose Injection, USP (5% dextrose) and the final concentration of pembrolizumab in the infusion solutions should be between 1.0 mg/mL and 10.0 mg/mL. Please note, the preferred diluent is 0.9% Sodium Chloride and 5% dextrose is only permissible if normal saline is not available. Administer infusion solution through an intravenous line containing a sterile, non-pyrogenic, low-protein binding 0.2 micron to 5 micron in-line or add-on filter.

Pembrolizumab should **NOT** be mixed with other diluents.

Parenteral drug products should be inspected visually for particulate matter and discoloration prior to administration. Discard the drug product vial if extraneous particulate matter other than translucent to white proteinaceous particles is observed.

Please **DO NOT**:

- **Use if discoloration is observed.**
- **Shake or freeze the vial(s).**
- **Administer the product as an (intravenous (iv) push or bolus).**
- **Combine, dilute or administer it as an infusion with other medicinal products.**

Further details on the preparation of the drug product can be found in the MSD pharmacy manual.

At each site the Investigator / designee e.g. pharmacist at each participating site is responsible for ensuring that all trial Medication must be stored in a secure, limited-access location under the storage conditions specified

Confidential

on the label. Receipt and dispensing of trial medication must be recorded by an authorized person at the trial site. Trial medication may not be used for any purpose other than that stated in the protocol.

6.3.4 Packaging and Labelling Information

Pembrolizumab will be supplied by Merck, Sharp and Dohme (MSD) as solution for injection. Pembrolizumab will be packaged, labelled and delivered to the participating sites free of charge by MSD. The IMP will be supplied specifically for the trial and should not be used for any other purpose than that stated in this protocol. The drug will be labelled in accordance to Good Manufacturing Practice Annex 13.

6.3.5 Returns and Reconciliation

The investigator / designee is responsible for keeping accountability accurate records for pembrolizumab including the amount dispensed to and returned by each patient and the amount remaining on site at the conclusion of the trial.

Upon completion or termination of the study, partially used trial medication will be destroyed at the site per institutional policy. It is the Investigator's/designees responsibility to arrange for disposal of all empty containers, provided that procedures for proper disposal have been established according to applicable local and institutional guidelines and procedures, and provided that appropriate records of disposal are kept.

Upon completion or termination of the study, all unused trial medication will be returned to MSD or destroyed at the site per institutional policy. It is the Investigator's/designees responsibility to arrange for disposal of all empty containers, provided that procedures for proper disposal have been established according to applicable federal, state, local and institutional guidelines and procedures, and provided that appropriate records of disposal are kept.

6.3.6 Doses and treatment regimens

All patients will receive pembrolizumab administered as per standard procedures following manufacturer's instructions. Two dose levels of pembrolizumab will be studied to ensure tolerability of combining therapy with chemoradiotherapy. The treatment regimen to be used at each dosing level is outlined in the table below.

Drug	Dose Level	Dose/ Potency	Dose Frequency	Route of Administration	Regimen/Treatment Period	Use
Pembrolizumab	1	100 mg	3-weekly	IV infusion	8 doses (pre treatment & 7 cycles)	Experimental
Pembrolizumab	2	200 mg	3-weekly	IV infusion	8 doses (pre treatment & 7 cycles)	Experimental
The pembrolizumab dosing interval may be increased due to toxicity as described in Section 6.3.9.2						

Table 9: Pembrolizumab treatment regimens for each dosing level.

6.3.7 Timing of Dose Administration

Trial treatment should be administered at the pre-loading dose and then on Day 1 of each cycle after all procedures/assessments have been completed as detailed in the Study Flow Chart (Section 3.4) and on the schedule of study assessment (Table 2). Trial treatment may be administered up to 3 days before or after the scheduled Day 1 of each cycle due to administrative reasons.

Cisplatin will be administered to the patient at a dose of 100 mg/m² with pre- and post-hydration as an in-patient. Therefore, the first 3 cycles of pembrolizumab will also be administered as an in-patient. Thereafter, all trial treatments will be administered on an outpatient basis. If the patient receives concomitant carboplatin (AUC = 5) rather than cisplatin, concomitant chemotherapy and study medication can be given as an outpatient.

Pembrolizumab will be administered as a 30 minute IV infusion (treatment cycle intervals may be increased due to toxicity as described in Section 6.3.9.2). Sites should make every effort to target infusion timing to be as close to 30 minutes as possible. However, given the variability of infusion pumps from site to site, a window of -5 minutes and +10 minutes is permitted (i.e., infusion time is 30 minutes: -5 min/+10 min).

The pharmacy manual contains specific instructions for pembrolizumab, reconstitution, preparation of the infusion fluid, and administration.

6.3.8 Trial Blinding/Masking

This is an open-label trial; therefore, the Sponsor, investigator and patient will know the treatment administered.

6.3.9 Dose Selection/Modification

6.3.9.1 Dose Selection

The rationale for selection of doses to be used in this trial is provided in Section 1.2.2 – Background and Rationale.

6.3.9.2 Dose Modification

Pembrolizumab will be withheld for drug-related Grade 4 hematologic toxicities, non-hematological toxicity ≥ Grade 3 including laboratory abnormalities (except for toxicities, such as mucositis, skin reaction, pain) that are commonly encountered during chemoradiotherapy for LA-SCCHN), and severe or life-threatening AEs as per the below table.

Toxicity	Hold Treatment For Grade	Timing for Restarting Treatment	Treatment Discontinuation
Diarrhea/Colitis	2-3	Toxicity resolves to Grade 0-1.	Toxicity does not resolve within 12 weeks of last dose or inability to reduce corticosteroid to 10 mg or less of prednisone or equivalent per day within 12 weeks.
	4	Permanently discontinue	Permanently discontinue
AST, ALT, or Increased Bilirubin	2	Toxicity resolves to Grade 0-1	Toxicity does not resolve within 12 weeks of last dose.
	3-4	Permanently discontinue (see exception below) ¹	Permanently discontinue

Toxicity	Hold Treatment For Grade	Timing for Restarting Treatment	Treatment Discontinuation
Type 1 diabetes mellitus (if new onset) or Hyperglycemia	T1DM or 3-4	Hold pembrolizumab for new onset Type 1 diabetes mellitus or Grade 3-4 hyperglycemia associated with evidence of beta cell failure.	Resume pembrolizumab when patients are clinically and metabolically stable.
Hypophysitis	2-4	Toxicity resolves to Grade 0- 1. Therapy with pembrolizumab can be continued while endocrine replacement therapy is instituted	Toxicity does not resolve within 12 weeks of last dose or inability to reduce corticosteroid to 10 mg or less of prednisone or equivalent per day within 12 weeks.
Hyperthyroidism	3	Toxicity resolves to Grade 0-1	Toxicity does not resolve within 12 weeks of last dose or inability to reduce corticosteroid to 10 mg or less of prednisone or equivalent per day within 12 weeks.
	4	Permanently discontinue	Permanently discontinue
Hypothyroidism		Therapy with pembrolizumab can be continued while thyroid replacement therapy is instituted	Therapy with pembrolizumab can be continued while thyroid replacement therapy is instituted.
Infusion Reaction	3-4	Permanently discontinue	Permanently discontinue
Pneumonitis	2	Toxicity resolves to Grade 0-1	Toxicity does not resolve within 12 weeks of last dose or inability to reduce corticosteroid to 10 mg or less of prednisone or equivalent per day within 12 weeks.
	3-4	Permanently discontinue	Permanently discontinue
Renal Failure or Nephritis	2	Toxicity resolves to Grade 0-1	Toxicity does not resolve within 12 weeks of last dose or inability to reduce corticosteroid to 10 mg or less of prednisone or equivalent per day within 12 weeks.
	3-4	Permanently discontinue	Permanently discontinue
All Other Drug-Related Toxicity ²	3 or Severe	Toxicity resolves to Grade 0-1	Toxicity does not resolve within 12 weeks of last dose or inability to reduce corticosteroid to 10 mg or less of prednisone or equivalent per day within 12 weeks.
	4	Permanently discontinue	Permanently discontinue

Note: Permanently discontinue for any severe or Grade 3 drug-related AE that recurs or any life-threatening event.

¹ For patients with liver metastasis who begin treatment with Grade 2 AST or ALT, if AST or ALT increases by greater than or equal to 50% relative to baseline and lasts for at least 1 week then patients should be discontinued.

² Patients with intolerable or persistent Grade 2 drug-related AE may hold study medication at physician discretion. Permanently discontinue study drug for persistent Grade 2 adverse reactions for which treatment with study drug has been held, that do not recover to Grade 0-1 within 12 weeks of the last dose.

Table 10: Dose Modification guidelines for drug-related adverse events.

In case toxicity does not resolve to Grade 0-1 within 12 weeks after last infusion, trial treatment should be discontinued. Patient's with a laboratory adverse event still at Grade 2 after 12 weeks may continue treatment in the trial only if asymptomatic and controlled. For information on the management of adverse events, see Section 7.

Patient's who experience a recurrence of the same severe or life-threatening event at the same grade or greater with re-challenge of pembrolizumab should be discontinued from trial treatment.

Radiotherapy-related adverse events will be managed as per institution clinical guidelines.

Events of Clinical interest (ECI) can be potential immune related adverse events and dose modifications for these toxicities should they occur can be found in appendix 5.

Dosing interruptions are permitted in the case of medical / surgical events or logistical reasons not related to study therapy (e.g., elective surgery, unrelated medical events, patient vacation, and/or holidays). Subjects should be placed back on study therapy within 3 weeks of the scheduled interruption, unless otherwise discussed with the Sponsor. The reason for interruption should be documented in the patient's study record.

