3.3 Dose Levels

This study has 2 dosing levels. The rate of entry and escalation to the next dose level will depend upon assessment of the toxicity profile of patients entered at the previous level. Toxicity and assessment for DLT period will be assessed during treatment and up until 6 weeks after the completion of chemoradiotherapy. The DLTs for this study will be defined as: Grade 4 thrombocytopenia (or Grade 3 with haemorrhage); Grade 4 neutropenia lasting >7 days (or Grade 3 with fever); Grade 4 anemia; Grade 4 mucositis (or Grade 3 with confluent lesions lasting >6 weeks after the end of radiotherapy); >2 weeks toxicity-related treatment delay; or any other \geq Grade 3 non-hematologic toxicity (except nausea and vomiting) which in the opinion of the investigator is considered dose-limiting. The results of each dosing level will be reviewed by the safety review committee (SRC) before recruitment to the next dose level can begin.

Escalation to the next dose level will not proceed until the following criteria are satisfied:

- **If 0/3 patients** experience any of the above mentioned DLT's escalation to the next dose level can proceed.
- **If 1/3 patients** experiences any of the above mentioned DLT's the dose level will be expanded to a total of 6 patients.
 - If 1/6 patients experience any of the above mentioned DLT's then escalation to the next dose level can proceed.
 - If \geq 2/6 patients in a specific dose level experience any of the above mentioned DLT's the maximum tolerated dose will have been reached and all subsequent patients will be recruited at the previous dose level.
- **If 2/3 patients** experience any of the above mentioned DLT's then the maximum tolerated dose will have been reached and the expansion cohort phase will begin at the previous dose level. If the MTD is reached at dose level 1 the study will be stopped.

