For Grade 2 pneumonitis that improves to ≤ Grade 1 within 12 weeks, the following rules should apply:

- First episode of pneumonitis
 - May increase dosing interval by one week in subsequent cycles
- Second episode of pneumonitis – permanently discontinue pembrolizumab if upon re-challenge patient develops pneumonitis ≥ Grade 2

Immune-mediated colitis

Monitor patients for signs and symptoms of colitis. Exclude other causes of colitis, and manage treatment in accordance with the guidelines above. Administer corticosteroids, withhold pembrolizumab for moderate (Grade 2) or severe (Grade 3) colitis, and permanently discontinue pembrolizumab for life-threatening (Grade 4) colitis.

Immune-mediated hepatitis

Monitor patients for changes in liver function (at the start of treatment, periodically during treatment and as indicated based on clinical evaluation) and symptoms of hepatitis. Exclude other causes of hepatitis, and manage treatment in accordance with the guidelines above. Administer corticosteroids and, based on severity of liver enzyme elevations, withhold or discontinue pembrolizumab.

Immune-mediated nephritis

Monitor patients for changes in renal function. Exclude other causes of nephritis, and manage treatment in accordance with the guidelines above. Administer corticosteroids, withhold pembrolizumab for moderate (Grade 2), and permanently discontinue pembrolizumab for severe (Grade 3) or life-threatening (Grade 4) nephritis.

Immune-mediated endocrinopathies

Monitor patients for signs and symptoms of hypophysitis (including hypopituitarism and secondary adrenal insufficiency). Exclude other causes of hypophysitis, and manage treatment in accordance with the guidelines above. Administer corticosteroids, withhold pembrolizumab for moderate (Grade 2), withhold or discontinue pembrolizumab for severe (Grade 3) and for life-threatening (Grade 4) hypophysitis.

Monitor patients for hyperglycemia or other signs and symptoms of type 1 diabetes. Administer insulin for type 1 diabetes, and withhold pembrolizumab in cases of severe hyperglycemia until metabolic control is achieved.

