Thyroid disorders have been reported in patients receiving pembrolizumab and can occur at any time during treatment; therefore, monitor patients for changes in thyroid function (at the start of treatment, periodically during treatment and as indicated based on clinical evaluation) and clinical signs and symptoms of thyroid disorders. Administer corticosteroids, withhold pembrolizumab for severe (Grade 3) hyperthyroidism, and permanently discontinue pembrolizumab for life-threatening (Grade 4) hyperthyroidism. Treat symptoms of hyperthyroidism as appropriate. Isolated hypothyroidism may be managed with replacement therapy without treatment interruption and without corticosteroids. For patients with severe (Grade 3) or life-threatening (Grade 4) endocrinopathy that resolved and is controlled with hormone replacement, continuation of pembrolizumab may be considered.

Other immune-mediated adverse events

Across clinical studies with pembrolizumab in approximately 5000 patients, the following additional clinically significant, immune-mediated adverse reactions were reported in less than 1% of patients: uveitis, [Guillain-Barre syndrome](#), and severe skin reactions.

In addition a set of irAEs have also been classified as immune-related events of clinical interest (irECI) a full list of these can be found in Appendix 5. Patients with symptomatic irECIs should immediately stop receiving pembrolizumab and be evaluated to rule out non treatment related causes of the event. Overdose and liver toxicity irECIs irrespective of relationship to the study drug should be reported within 24 hours of the investigator being aware to the Sponsor who will in turn notify MSD. If the irECI is determined to be associated please refer to Appendix 5 for the recommendations on the management of these irECIs. If the event is not considered to be associated with the study drug the physician should exercise individual clinical judgment on the event management based on the patient. Any additional questions of the collection or information on management of irECIs should be directed to the Sponsor.

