	Grade 2 – 4	
 Withhold pembrolizumab Rule out infection and sepsis. Monitor thyroid function until returned to baseline. Consider pituitary gland imaging Hypophysitis with clinically significant adrenal insufficiency and hypotension, dehydration, and electrolyte abnormalities (such as hyponatremia and hyperkalemia) constitutes adrenal crisis. Consider endocrinologist consult. 	
 Prednisone 40mg p.o. or equivalent per day. Symptoms grade 1 or less initiate steroid taper for no less than 4 weeks. Replacement of appropriate hormones may be required. Permanently discontinue pembrolizumab if dose cannot be reduced to prednisone 10mg or less or equivalent per day within 12 weeks.
Type 1 Diabetes Mellitus and ≥ grade 3 hyperglycaemia	Type 1 Diabetes Mellitus and ≥ grade 3 hyperglycaemia	
 Hold pembrolizumab if new onset of diabetes or grade 3-4 hyperglycaemia with evidence of beta cell failure. Consultation with endocrinologist Consider islet cell antibodies and antibodies 	
 Insulin replacement therapy is recommended for Type I diabetes mellitus and for Grade 3-4 hyperglycaemia associated with metabolic acidosis or ketonuria. Evaluate patients with serum glucose and a metabolic panel, urine ketones, glycosylated haemoglobin, and C-peptide.

		to GAD, IA-2 ZnT8 and insulin.	
Hematologic	Grade 1 (Asymptomatic)	
 No action 	
 Intervention not indicated
	Grade 2	
 Withhold pembrolizumab, may restart if Grade 1 or resolved within 12 weeks Consider Haematology consultation 	
 Prednisone 1-2mg/kg daily Permanently discontinue pembrolizumab if dose cannot be reduced to prednisone 10mg or less or equivalent per day within 12 weeks.
	Grade 3	
 Withhold pembrolizumab, may restart if Grade 1 or resolved within 12 weeks Recommend Haematology consultation 	
 IV methylprednisolone 125mg or Prednisone 1-2mg/kg p.o. (or equivalent) as appropriate. Permanently discontinue pembrolizumab if corticosteroid dose cannot be reduced to prednisone 10mg or less or equivalent per day within 12 weeks.

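### Grade 4 endocrine events carry conflicting pembrolizumab instructions: hold and resume in some places, permanent discontinuation in others

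*Combined protocol and SAP*

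**What the plan says.** Instructions on pembrolizumab after an endocrine event stand in several places.

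- **Table 10, hypophysitis row (section 6.3.9.2).** Hold at Grades 2-4. The restart cell gives recovery to Grade 0-1 as the condition and then adds "Therapy with pembrolizumab can be continued while endocrine replacement therapy is instituted".
- **Table 10, type 1 diabetes and hyperglycaemia row.** Hold for new-onset disease, or for Grade 3-4 hyperglycaemia with beta-cell failure. Resume once the patient is stable.
- **Table 10, hyperthyroidism row.** Hold at Grade 3; stop permanently at Grade 4.
- **Note under Table 10.** "Permanently discontinue for any severe or Grade 3 drug-related AE that recurs or any life-threatening event". Section 7.3.1 describes Grade 4 as life-threatening.
- **Text below Table 10.** A patient is taken off trial treatment when the same severe or life-threatening event returns, at the same or a higher grade, on re-challenge.
- **Section 6.6, endocrinopathies.** For hypophysitis: "withhold or discontinue pembrolizumab for severe (Grade 3) and for life-threatening (Grade 4) hypophysitis". For the thyroid: "permanently discontinue pembrolizumab for life-threatening (Grade 4) hyperthyroidism". Then, for Grade 3 or 4: "endocrinopathy that resolved and is controlled with hormone replacement, continuation of pembrolizumab may be considered".
- **Appendix 5 (section 12.5).** Withhold for Grade 2-4 hypophysitis, hold for new-onset diabetes or Grade 3-4 hyperglycaemia with beta-cell failure, discontinue for Grade 4 hyperthyroidism.

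The DLT list in section 3.3, repeated in section 12.1.4, includes ">2 weeks toxicity-related treatment delay" with no element of judgement. Any other non-haematological toxicity of Grade 3 or above (nausea and vomiting excepted) counts only if the investigator considers it dose-limiting.

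**The concern.** An investigator facing Grade 4 hypophysitis or Grade 4 hyperglycaemia can follow the event's own row and plan to resume, or follow the Note and stop for good. Both are in force, and the protocol does not say which governs. Two patients with the same event could be managed differently, each in line with the protocol. The first matter at stake is patient safety and consistent conduct.

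The second is conditional. The primary endpoint is the maximum tolerated dose, set by counting DLTs in groups of 3 to 6. If a pembrolizumab hold can count as a treatment delay, the choice of passage could decide whether an event is an automatic DLT or one left to opinion.

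**Working it through.** The plan states no figure on this point. Its sample-size range reproduces (3 × 2 cohorts = 6; (6 + 6 + 6) × 2 cohorts = 36) and is not affected. The check is therefore a comparison of passages.

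**Step 1. Grade 4 instructions side by side.**

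| Source | Hypophysitis | Hyperglycaemia with beta-cell failure | Hyperthyroidism |
|---|---|---|---|
| Table 10 row | Hold, restart at Grade 0-1; continuation sentence in same cell | Hold, then resume | Permanent stop |
| Table 10 Note with 7.3.1 | Permanent stop | Permanent stop | Permanent stop |
| Text below Table 10 | Stop on recurrence after re-challenge | Same | Same |
| Section 6.6 | Withhold or discontinue; continuation possible if resolved and controlled on replacement | Withhold if severe, until metabolic control | Permanent stop; the general continuation sentence is not limited to exclude it |
| Appendix 5 | Withhold; stop if steroids cannot be reduced within 12 weeks | Hold | Discontinue |

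For hypophysitis and hyperglycaemia, the row and the Note cannot both be followed at Grade 4.

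**Step 2. Does the Note bite anywhere else?** Every other graded row of Table 10, including the row for all other drug-related toxicity, already ends in permanent discontinuation at Grade 4. The rows that do not are hypophysitis, diabetes or hyperglycaemia, and hypothyroidism, whose row states no grade and lets treatment continue. So at Grade 4 the life-threatening limb of the Note changes the outcome only for endocrine events, which are the ones whose rows say otherwise.

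**Step 3. Consistency within section 6.3.9.2.** The text below Table 10 contemplates re-challenge after a life-threatening event and stops treatment if it recurs. The Note stops treatment at the first such event, so there would be no re-challenge.

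**Step 4. The continuation sentence.** It sits in the column on timing of restart. It can mean that treatment goes on during replacement therapy in place of a hold, or that treatment resumes on replacement after a hold. The cell does not say which.

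**Step 5. The conditional link to the DLT count.**

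- Chemoradiotherapy lasts 7 weeks and the DLT period runs 6 weeks beyond it: 7 + 6 = week 13. Doses fall at weeks -2, 0, 3, 6, 9, 12, 15 and 18, so 6 of the 8 lie within the period.
- If pembrolizumab counts as the delayed treatment, a hold of more than 2 weeks is an automatic DLT. A dose moved to the next 3-weekly visit would be 3 weeks late, though no passage requires a held dose to wait for that visit.
- If pembrolizumab is continued, a Grade 3 or higher event is a DLT only in the investigator's opinion. At Grade 2 no other listed criterion would apply.
- Permanent discontinuation is not literally a delay and is left unclassified.
- Under the 3+3 rule, one reclassified event turns 0/3 into 1/3 (escalate becomes expand to 6), or 1/6 into 2/6 (proceed becomes stop escalation; at dose level 1 the study ends).

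**Step 6. Which treatment does the clause mean?** For including pembrolizumab: Table 10 uses the word treatment for it in its column headings, section 6.3 calls it the trial treatment, and the one-week delay rule in section 12.1.3 follows text covering both platinum and pembrolizumab. Against: section 12.1.4 is headed as toxicity of chemoradiotherapy, the 14-day limit in section 12.1.3 is for cisplatin or carboplatin, and Appendix 1 modifies only the responsible agent where the cause is clear. The text does not settle it.

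**The case against.** Much of the text can be harmonised by a sympathetic reader.

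- **Hold, then resume.** Because the continuation sentence stands in the restart column, the hypophysitis row can be read in sequence, and it then agrees with Appendix 5. This is a fair reading and may be the intended one. It removes the conflict within the row but not the conflict with the Note.
- **Section 6.6 has a rule for choosing.** Its hypophysitis paragraph refers back to earlier guidelines. Table 12 withholds at Grades 3-4 and stops if steroids cannot be reduced within 12 weeks. That helps, but Table 12 is introduced for events not covered elsewhere, and hypophysitis is covered elsewhere.
- **The specific row overrides the general Note.** This is sensible drafting practice, but the protocol does not state it. By step 2, it would leave the life-threatening limb of the Note with nothing to do at Grade 4.
- **Hyperthyroidism is consistent.** Its Table 10 row, its sentence in section 6.6 and its Appendix 5 row all stop permanently at Grade 4, and none of them tells the investigator to hold. A reader might infer that every Grade 4 endocrine event is told to hold, continue and stop at once; the documents do not support that. For hyperthyroidism the tension is only with the permissive general sentence in section 6.6.
- **The DLT list has a safeguard.** Grade 3 or higher events can already be counted by investigator opinion, and the safety committee reviews each dose level. This stands, so any effect is on automatic classification.

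**Conclusion.** The contradiction is real and specific. At Grade 4, the Table 10 Note conflicts with the hypophysitis and hyperglycaemia rows and with Appendix 5. It also conflicts with the re-challenge text below the table and with the continuation sentence in section 6.6. The wording of the hypophysitis restart cell is ambiguous. This is an internal inconsistency, not a design choice, and it matters for safety whatever is decided about DLTs.

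The effect on the primary endpoint is possible but not established. It needs three things: the delay clause must include pembrolizumab, the hold must exceed 2 weeks, and it must fall within the DLT period. If the clause covers chemoradiotherapy only, a hold of pembrolizumab alone never triggers it, whichever passage is followed.

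Two further inferences should be resisted. A reader might take the steroid taper in Appendix 5, "Symptoms grade 1 or less initiate steroid taper for no less than 4 weeks", as showing that the hold exceeds the 2-week threshold. It does not: Table 10 allows restart when "Toxicity resolves to Grade 0-1", which is nearly the same trigger as the start of the taper, and no passage requires hypophysitis patients to be held until the taper ends. A reader might also want a figure for the loss in the chance of clearing a dose level. Any such figure would rest on assumed rates, because the documents give neither an endocrine event rate nor a DLT rate.

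**What to change.** Reconcile the Table 10 endocrine rows, the Table 10 Note, the re-challenge text below the table, the endocrine part of section 6.6 and Appendix 5, so that each endocrine event and grade has one instruction. State which passage governs if any overlap remains. Reword the continuation sentence in the hypophysitis restart cell so that it has one meaning. The clinical rule itself is for the investigators to choose.

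In sections 3.3 and 12.1.4, state which treatment's delay counts towards the 2-week criterion, and how a protocol-directed hold or permanent discontinuation of pembrolizumab is classified. The DLT count then does not depend on the passage followed.

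The cost is a wording amendment. It needs no new data or visits and leaves the sample size unchanged.
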